Slow release from sublingual fat depots prolongs the drug's effect, typically providing effective analgesia lasting up to 3 hours – a sufficient window within which to treat pain in the ER or for ambulatory surgery. Sufentanil has no active metabolites that “stack” its effects or contribute to side effects. Available literature remains sparse, making it well worth examining the potential benefits of sublingual sufentanil on post-operative recovery, especially the extent to which sublingual sufentanil might provide safe and effective analgesia for minor ambulatory surgery.

Objectives:

Objective: A pilot study to evaluate the effect of incorporating sublingual sufentanil into our perioperative opioid regimen for ambulatory orthopedic surgery. The results will help us estimate treatment effect and determine sample size for a subsequent full-scale clinical trial.

Primary Endpoint: total amount of fentanyl consumed during PACU admission.

Secondary Endpoints: 1) phase I recovery time; and, 2) time to fitness for discharge.

Exploratory Endpoints: 1) intraoperative hemodynamics 2) intraoperative opioid use; 3) intraoperative sevoflurane use 4) postoperative pain; 5) time to first request for analgesia;

and, 6) incidence of nausea and vomiting between end of anesthesia and hospital discharge.

Safety Monitoring: all adverse events will be recorded as detailed below.

Methods

A pilot for a randomized, controlled trial.

Subject selection

Study coordinators at Fairview Hospital will call patients scheduled for knee arthroscopy at least 1 day prior to the day of surgery to notify them of eligibility with the use of an IRB approved phone script (to be submitted in a supplemental document not contained in the protocol). Interested patients will be met in the facility on the day of surgery to provide private consultation, wherein the purpose, objectives, risks, and benefits of the investigation will be thoroughly addressed. Signed copies of the consent form will be stored on-site in a secure location.

Team consensus from the PI, anesthesiologist, and the patient's surgeon regarding research enrollment will be obtained. Each team member must agree as to the suitability for research and safety of the intervention as it pertains to each case. Communication will be documented in the electronic medical record system.

Inclusion Criteria:

- Adults aged ≥ 18 years;
- Scheduled for elective knee arthroscopy without anticipated ligamentous repair;

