- 2) Phase I recovery time: per anesthesia record, the time documented for end-of-case will be taken as the time that the patient entered phase I recovery. Recovery will be considered complete at the time an order is placed for progression to phase II, limiting the extent to which PACU traffic and bed availability can affect the assessment. Determination of phase I discharge readiness is made at regular intervals according to criteria detailed in Cleveland Clinic's Routine Postoperative Patient Care Protocol.
- 3) Time to Fitness for PACU Discharge: will be determined per facility protocol-scheduled assessments using the CCF Phase II Discharge Scoring tool. The time that the minimum acceptable score of 14 is achieved will be recorded.
- 4) Intraoperative Hemodynamics: the incidence of induction hypotension as measured by the area under a MAP of 65 mmHg during the initial 15 minutes of anesthesia.
- 5) Intraoperative IV Opioid Use: amount of clinically indicated opioid outside of standardized anesthetic regimen, in oral morphine equivalents (OME).
- 6) Intraoperative Sevoflurane Use
- 7) Postoperative Pain Score: measured as 0-10 Verbal Response Scores conducted at rest.
- 8) Postoperative Sedation and Cognitive Recovery: there is no validated scoring tool which assesses cognitive recovery after anesthesia in ambulatory surgery. Still, there may be value in trying to elucidate an approximation in this trial given anecdotal evidence that sufentanil reduces the use of intraoperative anesthetic gas and promotes faster recovery to arousal/cognitive baseline. To measure this, first RASS will be utilized by a member of the staff to capture early recovery while patients are less able (or unable) to answer questions. When a patient is no longer

sedated according to RASS and able to “spontaneously pay attention”, the BOMC test will be administered to measure improvements in executive cognitive functions thereafter.

9) Time to first request for analgesia: defined as the time from official case end until the first recorded Verbal Response Pain Score of greater than 4 (necessitating intervention).

10) Incidence of post-operative nausea/vomiting: the number of cases identified as clinically significant PONV using the PONV Intensity Scale.

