Opioid-related adverse events will be recorded, including nausea and vomiting and respiratory depression requiring treatment (naloxone, airway support, etc.). Adverse event reporting will proceed in accordance with Cleveland Clinic IRB-60 Policy.

Data analysis

Randomized groups will be compared for baseline balance using standard descriptive statistics and the standardized difference (difference in means or proportions divided by the pooled standard deviation).

Firstly, we will describe and plot the distribution of the primary outcome, which is the total amount of fentanyl consumed during PACU. If the distribution is approximately normal, we will calculate the standard deviation directly; if it is log-normal, we will estimate the geometric mean and the coefficient of variance. Then we will assess the effect of treatment using t-test or linear regression after log transformation as appropriate.

To assess the treatment effect on Phase I recovery time and time to fitness for discharge, we will use t-test or Wilcoxon test, depending on the distribution of the outcome variables. The difference in mean or median will be reported with 95% confidence interval.

Exploratory outcomes will be summarized by treatment group. The pain level will be summarized by time and the difference across all times will be summarized as difference in mean with 95% confidence interval; the difference in time to first request for analgesia will be summarized as median difference with 95% confidence interval; difference in nausea and vomiting will be summarized as relative risk with 95% confidence interval.

The overall alpha will be 0.05 for both primary and secondary outcomes. Thus the significance level is 0.05 for the primary outcome and 0.025 (i.e. 0.05/2, Bonferroni correction) for all secondary outcomes.

Sample size and power consideration

As this is a pilot study, we aim to estimate the standard deviation of various outcomes, but not to achieve statistical significance. Pilot trial recommendations are usually for 30 to 70 patients [5]. We thus propose to enroll 75 patients, excluding up to 6 pilot patients.

References:

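### Testing each of the two secondary outcomes at a fixed 0.025 is valid, but Holm's procedure gives somewhat more power under the same 0.05 familywise bound (low priority)

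*Combined protocol and SAP*

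**What the plan says.** The Objectives section of the combined protocol and SAP lists two secondary endpoints: "phase I recovery time; and, 2) time to fitness for discharge". For both, the Data analysis section states that "we will use t-test or Wilcoxon test, depending on the distribution of the outcome variables". On multiplicity it says: "The overall alpha will be 0.05 for both primary and secondary outcomes". It then gives 0.05 to the primary outcome and "0.025 (i.e. 0.05/2, Bonferroni correction) for all secondary outcomes". No step-down, hierarchical or gatekeeping rule appears anywhere.

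The same section says of the secondary results: "The difference in mean or median will be reported with 95% confidence interval". The next section, on sample size and power, explains that the pilot is meant to estimate standard deviations and is not designed to reach significance. It gives no effect size and no power target.

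**The concern.** A single-step Bonferroni rule holds both tests at 0.025 even after one of them has succeeded. Holm's rule compares the smaller p-value with 0.025 and, if that test rejects, compares the other with 0.05. It protects the same familywise level and can only add rejections.

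What is at stake is power for the second of the two recovery outcomes. The trial has only 25 controls, and the natural question is whether both recovery milestones improve. Since the plan writes down a formal testing rule for these outcomes, there is little reason to choose the one that rejects less.

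**Working it through.** **Inputs from the documents.** Two secondary outcomes with a familywise level of 0.05 for the pair (Objectives; Data analysis). 25 control and 50 sufentanil patients (Randomization). t-test or Wilcoxon test (Data analysis).

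**Assumed, because the documents do not state them.** Two-sided tests, normal outcomes, no dropout, standardized effects of 0.5 to 0.8 SD, and correlation between the outcomes of 0 to 0.9.

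**The plan's own figure.** 0.05 / 2 = 0.025. This reproduces exactly. If the tests were independent, the familywise error would be 1 − (1 − 0.025)² = 0.0494. The stated level is therefore correct.

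**Holm's bound.** Two cases are enough.
- Both nulls true: Holm makes a false rejection only if the smaller p-value is at most 0.025. The probability of that is at most 0.025 + 0.025 = 0.05, and the event is the same as under Bonferroni.
- One null true: a false rejection requires that outcome's p-value to be at most 0.05, so the probability is at most 0.05.

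Neither case uses the correlation. The argument also holds for Wilcoxon p-values.

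**Where the gain comes from.** The two rules differ only when one p-value is at most 0.025 and the other lies between 0.025 and 0.05. Bonferroni then rejects one outcome and Holm rejects both. It follows that the chance of at least one rejection is unchanged. With equal effects, the gain per outcome is half the gain for both.

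**Size, by simulation.** 200,000 trials per scenario, 25 v 50 patients, bivariate normal outcomes, pooled t-tests with 25 + 50 − 2 = 73 degrees of freedom. Effects of 0.5 SD on both outcomes:

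| Correlation | Per outcome, Bonferroni → Holm | Both outcomes, Bonferroni → Holm | At least one, either rule |
|---|---|---|---|
| 0.5 | 40.8% → 45.5% | 24.4% → 34.0% | 57.0% |
| 0.7 | 40.5% → 45.2% | 28.1% → 37.4% | 52.9% |
| 0.9 | 40.9% → 45.0% | 33.7% → 42.0% | 47.9% |

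The gains are about 4 to 5 points per outcome and about 8 to 10 points for both, in the expected one-to-two ratio. Across equal effects of 0.5 to 0.8 SD and correlations of 0 to 0.9, the ranges are about 3 to 6.5 points per outcome and about 6 to 13 points for both.

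With unequal effects of 0.7 and 0.5 SD at correlation 0.7, power for the weaker outcome rises from 41% to 50%, and the stronger outcome gains only about 1.5 points.

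**Actual error.**
- Both nulls true: identical under the two rules, at 0.046, 0.043 and 0.036 for correlations 0.5, 0.7 and 0.9.
- One null true, 0.6 SD on the other outcome: about 0.025 under Bonferroni and 0.037 to 0.038 under Holm.
- One null true, 0.7 SD on the other outcome: 0.025 under Bonferroni and 0.037 to 0.041 under Holm.

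**The case against.** The strongest defence is that nothing here is wrong. Bonferroni for two outcomes is valid, correctly computed and pre-specified, and the pilot says that significance is not its aim. Holm would change no standard deviation, no effect estimate and no reported interval, so it leaves untouched what the pilot is meant to deliver for the later trial. This stands, and it is why the priority is low. It does not remove the point, because the plan still commits to formal tests of these outcomes at a stated level.

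A second defence is that Bonferroni pairs simply with 97.5% intervals and Holm has no equally simple counterpart. That is a real advantage, but the plan does not use it. Its 95% intervals do not match a 0.025 test: such an interval can exclude zero when the p-value lies between 0.025 and 0.05.

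Two stronger readings are tempting, and the documents do not support either.
- A reader might infer that the two times overlap and that Bonferroni is wasteful for that reason. Phase I recovery has a stated start ("the time documented for end-of-case will be taken as the time that the patient entered phase I recovery") and a stated end ("Recovery will be considered complete at the time an order is placed for progression to phase II"). For fitness for discharge, the Measurements section gives only the end: "The time that the minimum acceptable score of 14 is achieved will be recorded". Overlap is therefore an inference. It is also not the source of Holm's advantage: at 0.6 SD on both, the gain per outcome is about 6.1 points at correlation 0 and 4.4 points at 0.9.
- A reader might infer that Bonferroni's extra strictness buys no error control at all. That is true of the 0.05 bound and of the case where both nulls hold. When one null is true, Bonferroni's actual error is lower.

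**Conclusion.** The point holds as an efficiency improvement. It is not an error in the plan. That Holm rejects at least as much within the same 0.05 familywise bound needs no assumption about effects or correlation. The size of the gain does: every power figure rests on assumed effects, correlations and normality, none of which the documents give. The gain lies wholly in the second rejection, and it is paid for by a higher actual error, still within the bound, when only one outcome is truly affected. Because the pilot disclaims significance as an aim, this is a low-priority change that is worth making mainly because it is cheap.

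**What to change.** In the Data analysis section, replace the rule for the secondary outcomes with: *The two secondary outcomes will be tested with Holm's procedure at a familywise level of 0.05; the 95% confidence intervals are descriptive and not adjusted for multiplicity.* The primary test at 0.05 stays as it is.

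The cost is one sentence, with no extra patients or data. The second clause also settles how the 95% intervals relate to the tests. The downside is the lack of a simple interval for each step-down decision. If the sponsor would rather have matching intervals, keeping Bonferroni and reporting 97.5% intervals is a coherent alternative.
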